6. STATISTICAL ANALYSES

6.1. **Demography**

6.1.1. **Analysis of demographics/baseline characteristics planned in the protocol**

The analysis of demographics will be performed on the ES and on the PPS for immunogenicity.

Demographic characteristics such as age at vaccination in years, race, ethnicity, vital signs and cohort description will be summarised by group using descriptive statistics:

- Frequency tables will be generated for categorical variable such as race.
- Mean, median, standard error and range will be provided for continuous data such as age.

The distribution of subjects will be tabulated as a whole and per group and for each age category (18 - 32 years and 33 - 45 years).

Withdrawal status will be summarised by group using descriptive statistics:

- The number of subjects enrolled into the study as well as the number of subjects excluded from PPS analyses will be tabulated.
- The number of withdrawn subjects will be tabulated according to the reason for withdrawal.

6.1.2. Additional considerations

- Vital signs will be presented at all time point(s) the information is collected on Exposed Set and Per Protocol Set.
- Summary of important protocol deviation leading to elimination will be presented. An individual listing will also be presented for this.
- The following table will be performed for web public disclosure
 - Percentage of Enrolled subjects by country will be tabulated by group,
 - Percentage of Enrolled subjects by age categories (18 - 64 years) will be tabulated by group.

6.2. Exposure

6.2.1. Analysis of exposure planned in the protocol

None

6.3. Immunogenicity

6.3.1. Analysis of immunogenicity planned in the protocol

The analysis will be performed on the applicable PPS cohort for immunogenicity and, if in any group the percentage of vaccinated subjects with serological results excluded from the PPS for analysis of immunogenicity is $\geq 5\%$, a second analysis will be performed on the ES.

6.3.1.1. Within group assessment

Humoral Immune response to RSV vaccine

For each group, at each time point that blood samples are collected and for each assay (RSV-A NAb and RSVPreF3 IgG) (unless specified otherwise):

- GMTs/GMCs will be tabulated with 95% CI based on log-transformed values and represented graphically.
- Percentage of subjects above the sero-positivity threshold will be tabulated with exact 95% CI.
- Pre- and Post- titres/concentrations will be displayed using reverse cumulative curves.
- The distributions of RSV-A NAb titres (Percentage of subjects greater than or equal to specified thresholds (< 128, 128-256, > 256-512, > 512-1024, > 1024-2048, > 2048-4096, >4096-8192 and >8192) will be tabulated.

- Individual post-vaccination versus pre-vaccination results will be plotted using scatter plots. Results of the control group will be used as a reference.
- Geometric mean of ratios of antibody titres/concentrations post-vaccination over pre-vaccination will be tabulated with 95% CI.
- Distribution of the fold increase of the antibody titres (post- over pre-vaccination titers) will be tabulated.
 - Percentage of subjects with a fold increase equal to or above 2, 4, 6, 8, 10 and 12 by pre-vaccination titre category: (< 128, 128-256, > 256-512, > 512-1024, > 1024-2048, > 2048-4096, > 4096, and by cumulative category: <128, \geq 128, \geq 256, \geq 512, \geq 1024, \geq 2048, \geq 4096.).
- The kinetics of individual antibody titres/concentrations will be plotted as a function of time for subjects with results available at all time points.
- An analysis of variance model for repeated measures will be fitted to assess the mean profile in each group.

If deemed necessary (minimum of 10% subjects is required in both the age-category), the same analyses may be performed by age category (18 - 32 years and 33 - 45 years).

Fold increase of RSVPreF3 immunoglobulin G (IgG) antibody concentrations over fold increase of RSV-A Nab titres (Ratio of fold increase Post- over Pre-vaccination) will be tabulated using descriptive statistics. This analysis will include calculation on:

- Geometric mean ratios with corresponding 95% CIs of RSVPreF3 immunoglobulin G (IgG) antibody concentration over anti-RSV-A plaque reduction Nab titres at pre-vaccination for each group and
- Geometric mean ratios with corresponding 95% CIs of fold increase post/pre (Day 8, Day 31, Day 61 and Day 91/Day 1) between RSVPreF3 immunoglobulin G (IgG) antibody concentration and anti-RSV-A plaque reduction Nab titres for each group

6.3.1.2. Between group assessment

Exploratory comparisons will be performed for RSV-A Nab titres and RSVPreF3 IgG antibody concentrations between the different RSV vaccine groups at Day 31. If deemed necessary, this exploratory comparison may also be done at other time-points.

- The three RSV formulations will be first compared to the Placebo in order to identify groups whose means are significantly different from the mean of the Placebo group, (alpha=2.5%, Dunnett's adjustment test for multiplicity). The model will include vaccine group as fixed effect, pre-vaccination titre/concentration. Age categories (18 - 32 years and 33 - 45 years) and/or centre will be added as the categorical covariate, if deemed necessary and is significant. For this analysis, the model will be explored and fitted via the proc mixed procedure according to the following code:

```
PROC MIXED data=sero;
CLASS subjid group age_cat center;
MODEL log_val = baseline group age_cat center
/ddf=kenwardroger outp = pred;
Random Subjid;
lsmeans group/pdiff=control('1') adjust=dunnett cl alpha=0.05;
RUN;
```

- Estimation of GMT/GMC ratios between groups with corresponding 95% CI using an ANCOVA model on the logarithm10 transformation of the titres/concentrations. This model includes:
 - The vaccine group as the fixed effect
 - The pre-vaccination titre/concentration as the covariate
 - Age groups (18 - 32 years and 33 - 45 years) and/or centre as the categorical covariate if deemed necessary
- Linear and quadratic trend of dose response will be tested using appropriate contrasts.

For the between group analysis among groups and trend tests, the model will be explored and fitted via the proc mixed procedure according to the following code:

```
PROC MIXED data=sero;
CLASS subjid group age_cat center;
MODEL log_val = baseline group age_cat center
/ddf=kenwardroger outp = pred;
Random Subjid;
lsmeans group/pdiff, cl alpha=0.05;
ods output diffs = diff lsmeans = lsm covparms=cov;
Contrast 'Linear' group 0 -4 -1 5;
Contrast 'Quadratic' group 0 -3 1 2;
RUN:
```

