10. LIST OF FINAL REPORT TABLES, LISTINGS AND FIGURES

The TFL TOC provides the list of tables/listings and figures needed for the study report. It also identifies the tables eligible for each analyses and their role (synopsis, in-text, post-text, SHS, CTRS,...). Note that all TFL aimed to be included as post-text are noted as post-text even if these are tabulation of individual data such as listing of SAE. The post-text material contains all source material for the study report and accordingly a post-text table may be redundant with an in-text table.

The following group names will be used in the TFLs, to be in line with the T-domains:

Group order in tables	Group label in tables	Group definition for footnote
1	RSV MAT 30	Subject receiving RSVPreF3 low dose
2	RSV MAT 60	Subject receiving RSVPreF3 mid dose
3	RSV MAT 120	Subject receiving RSVPreF3 high dose
4	Placebo	Subject receiving placebo

The following sub-group names will be used in the TFLs

Sub-group order in tables	Sub-group label in tables	Sub-group definition for footnote
1	18-32Y	Subjects 18-32 years of age
2	33-45Y	Subjects 33-45 years of age

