95% CI = 95% confidence interval for the GMT/GMC ratio (ANCOVA model: adjustment for age_cat, center and baseline titre - pooled variance), LL = lower limit, UL = upper limit

Age_cat is 1 for subject within age interval of 18-32 years and 2 for 33-45 years

Template 49 Exploratory comparisons (<GMT, GMC> ratios) between RSV groups and placebo with corresponding 95% confidence interval for <RSV A neutralizing antibody titre, RSV F IgG antibody concentration> at Day 31 <PPS for immunogenicity at Day 31>

								GMT ratio				
										Adjusted 95% CI	Adjusted p-value	
Antibody	Timepoint	Group description	N	<GMT, GMC>	Group description	N	<GMT, GMC>	Ratio order	Value	LL	UL	
<RSV-A NAb, RSV IgG antibody>	PI(D8)	RSV MAT 120			Placebo			RSV MAT 120/Placebo				
		RSV MAT 60			Placebo			RSV MAT 60/ Placebo				
		RSV MAT 30			Placebo			RSV MAT 30/Placebo				

RSV MAT 30 = Subject receiving RSVPreF3 low dose

RSV MAT 60 = Subject receiving RSVPreF3 mid dose

RSV MAT 120 = Subject receiving RSVPreF3 high dose

Placebo = Subject receiving placebo

Adjusted GMT = geometric mean antibody titre adjusted for age_cat, center and baseline titre

N = Number of subjects with both pre- and post-vaccination results available

95% CI = 95% confidence interval for the GMT/GMC ratio (ANCOVA model: adjustment for age_cat, center and baseline titre - pooled variance), LL = lower limit, UL = upper limit

P-values were adjusted according to Dunnett for multiple comparisons to placebo

Age_cat is 1 for subject within age interval of 18-32 years and 2 for 33-45 years

PI(D31) = Post-vaccination at Day 31

Template 50 Descriptive statistics of <anti-RSV A neutralizing antibody titre, anti-RSV F IgG antibody concentration>at pre-vaccination, Day <8, 31, 61, 91><PPS for immunogenicity>

Visit	Parameters	Each Group		95% CI
		N=	LL	
PRE	N with data			
	Mean			
	SD			
	Q1			
	Median			
	Q3			
PI(D8)	...			
PI(D31)	...			
PI(D61)	...			
PI(D91)	...			

<each group>:

RSV MAT 30 = Subject receiving RSVPreF3 low dose

RSV MAT 60 = Subject receiving RSVPreF3 mid dose

RSV MAT 120 = Subject receiving RSVPreF3 high dose

Placebo = Subject receiving placebo

N = total number of subjects

N with data = number of subjects with available results

Value = value of the considered parameter

SD = standard deviation

Q1 and Q3 = 1st and 3rd quantiles

LL, UL = Exact 95% Lower and Upper confidence limits

PRE = Pre-vaccination at screening

PI(D8) = Post-vaccination at Day 8

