PI(D31) = Post-vaccination at Day 31

PI(D61) = Post-vaccination at Day 61

PI(D91) = Post-vaccination at Day 91

Template 51 Descriptive statistics of area under the curve up to Day 91 for <anti-RSV A neutralizing antibody titre, anti-RSV F IgG antibody concentration> 91><PPS for immunogenicity>

Timepoint	Parameters	Each Group	
		N=	95% CI
Up to Day 91	N with data		
	Mean		
	SD		
	Q1		
	Median		
	Q3		

<each group>:

RSV MAT 30 = Subject receiving RSVPreF3 low dose

RSV MAT 60 = Subject receiving RSVPreF3 mid dose

RSV MAT 120 = Subject receiving RSVPreF3 high dose

Placebo = Subject receiving placebo

N = total number of subjects

N with data = number of subjects with documentation of the corresponding data

Value = value of the considered parameter

SD = standard deviation

Q1 and Q3 = 1st and 3rd quantiles

LL, UL = Exact 95% Lower and Upper confidence limits

Template 52 Assessment of trend (linear or quadratic) of dose response for <<anti-RSV A neutralizing antibody titre, anti-RSV F IgG antibody concentration> between three RSV vaccine groups at Day 31 <PPS for immunogenicity at Day 31>

Antibody	Trend Test	N	P value
<Anti-RSV A Neutralizing Antibody, RSV IgG antibody>	Linear		
	Quadratic		

<each group>:

RSV MAT 30 = Subject receiving RSVPreF3 low dose

RSV MAT 60 = Subject receiving RSVPreF3 mid dose

RSV MAT 120 = Subject receiving RSVPreF3 high dose

Analysed using ANCOVA fitting treatment as fixed effect and age_cat, center and baseline titre as covariate

Contrast used for evaluating <linear,quadratic> trend is

Age_cat is 1 for subject within age interval of 18-32 years and 2 for 33-45 years

Template 53 Assessment of trend (linear or quadratic) of dose response using area under curve up to Day 91 for <<anti-RSV A neutralizing antibody titre, anti-RSV F IgG antibody concentration> between three RSV vaccine groups <PPS for immunogenicity>

Antibody	Trend Test	N	P value
<Anti-RSV A Neutralizing Antibody, RSV IgG antibody>	Linear		
	Quadratic		

<each group>:

RSV MAT 30 = Subject receiving RSVPreF3 low dose

RSV MAT 60 = Subject receiving RSVPreF3 mid dose

RSV MAT 120 = Subject receiving RSVPreF3 high dose

Analysed using ANCOVA fitting treatment as fixed effect and age_cat, center and baseline titre as covariate

Age_cat is 1 for subject within age interval of 18-32 years and 2 for 33-45 years

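### The SAP's between-group code assumes placebo is level 1, which it never defines and its only group numbering contradicts; no level order makes both trend contrasts correct

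*SAP*

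**What the plan says.** SAP 6.3.1.2 describes the first between-group step as follows: "The three RSV formulations will be first compared to the Placebo in order to identify groups whose means are significantly different". The printed code for that step is "lsmeans group/pdiff=control('1') adjust=dunnett cl alpha=0.05". The table shell, Template 49, has rows for 120, 60 and 30 µg over placebo and the footnote "P-values were adjusted according to Dunnett for multiple comparisons to placebo".

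The same section then tests linear and quadratic dose trends with "Contrast 'Linear' group 0 -4 -1 5" and "Contrast 'Quadratic' group 0 -3 1 2". Template 52 limits the trend to the "three RSV vaccine groups at Day 31 <PPS for immunogenicity at Day 31>", so placebo is meant to be left out. SAP 6.3.2 applies a similar program to the area under the curve (AUC) up to Day 91, reported in Template 53.

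The only place where the SAP numbers the groups is section 10, introduced by "The following group names will be used in the TFLs, to be in line with the T-domains". There 1 = RSV MAT 30, 2 = RSV MAT 60, 3 = RSV MAT 120 and 4 = Placebo. The coding of `group` in the analysis dataset `sero` is not given anywhere.

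The text also states "alpha=2.5%, Dunnett's adjustment test for multiplicity" without saying whether the level is one- or two-sided.

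**The concern.** SAS applies `control('1')` to the level whose value is 1, and applies contrast coefficients in the sorted order of the CLASS levels. Both therefore depend on how `group` is coded. A programmer who takes the coding from the only numbering in the SAP gets code that runs cleanly and answers different questions.

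The trend test is the more exposed part. Templates 52 and 53 show the trend name, N and a p-value, with no estimate or sign, so a vaccine-versus-placebo difference could be read as a dose trend. The trend results bear on how response changes between 30, 60 and 120 µg for two assays, at Day 31 and for AUC.

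A second problem does not depend on the coding: the quadratic coefficients do not measure curvature over these doses when the levels run Placebo, 30, 60, 120.

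**Working it through.** **Inputs.** Doses 30, 60, 120 µg (SAP 3.1). About 125 subjects per group and SD of log10 RSV-A Nab 0.4, with 0.3 to 0.5 as the range shown (Protocol 10.4). Coefficients from SAP 6.3.1.2. The rise over placebo is not given in the documents; 2-fold to 8-fold is assumed. Covariates are ignored and a normal approximation is used.

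**1. Reproduce the linear coefficients.** The mean dose is (30 + 60 + 120)/3 = 70. Centred doses are -40, -10, 50, that is -4 -1 5. This matches the SAP exactly, provided the levels run Placebo, 30, 60, 120.

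**2. Derive the quadratic.** Weights a, b, c on 30, 60, 120 must satisfy a + b + c = 0 and 30a + 60b + 120c = 0. Hence b = -3c and a = 2c, giving 2 -3 1. The SAP has -3 1 2 in those positions.
- Applied to dose itself: -3×30 + 1×60 + 2×120 = 210, where a quadratic contrast must give 0.
- Dot product with the linear: (-4)(-3) + (-1)(1) + (5)(2) = 21.
- Correlation: 21/√(42×14) = 0.87.
- A log-dose scale does not explain it: the quadratic would then be 1 -2 1.

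**3. Is there an order that suits both?** Both contrasts put 0 first, so placebo must be first. The linear then needs 30, 60, 120. The quadratic needs -3 on 60, 1 on 120 and 2 on 30, that is the order 60, 120, 30. These differ, so no order makes both right.

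**4. Effect of the quadratic error under placebo-first coding.** Take the 2-fold rise from low to high dose that Protocol 10.4 considers, and assume log10 titre is exactly linear in dose. Means relative to 30 µg are 0, 0.301×30/90 = 0.100, and 0.301.
- Printed quadratic: 0.100 + 2×0.301 = 0.702. SE = 0.4×√(14/125) = 0.134, so z = 5.2, significant in over 99% of trials at two-sided 5%.
- Quadratic 2 -3 1: -3×0.100 + 0.301 = 0, as it should be.

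**5. Effect of the section 10 numbering on the trend test.** The linear contrast becomes 5×Placebo - 4×MAT60 - MAT120. With all three doses equal and 2-fold above placebo:
- Estimate: -5×0.301 = -1.505 instead of 0.
- SE = SD×√(42/125): 0.174, 0.232 and 0.290 for SD 0.3, 0.4 and 0.5.
- z = -8.7, -6.5 and -5.2.
- With an 8-fold rise and SD 0.4, z = -4.515/0.232 = -19.5.

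Across a 2- to 8-fold rise and SD 0.3 to 0.5, a flat dose response is declared a linear trend in at least 99.9% of trials, where 5% is intended. The quadratic rejects in 95% to 100%.

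**6. Effect of the section 10 numbering on the Dunnett step.** MAT60, MAT120 and Placebo are each compared with MAT30. Only 30 µg versus placebo survives, with its sign reversed; 60 and 120 µg are not compared with placebo.

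**7. Text labels.** These sort as Placebo, RSV MAT 120, RSV MAT 30, RSV MAT 60. The linear contrast then has dot product 4 - 5 - 20 = -21 with the intended one, a correlation of -21/42 = -0.5.

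**The case against.** The strongest reply is that section 10 sets the order of groups for display in tables, not the coding of the dataset. Within SAP 6.3.1.2 the text, the control level and the linear weights all agree on placebo first, so an undocumented placebo-first code is the natural reading. This stands. A reader might infer that the printed code tests the wrong groups; the documents do not establish that, because they never say how `group` is coded.

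A wrong Dunnett reference would also probably be noticed. Template 49 needs 60/Placebo and 120/Placebo rows, which a run against 30 µg would not produce, and SAP 8.1 calls for a dry run review of every analysis. That stands for the Dunnett step. It protects the trend test less: Template 52 has a footnote for the contrast used, but coefficients without the level order would not expose a mismatch.

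SAP 6.3.1.2 calls the comparisons exploratory, and SAP 7 calls all comparative analyses descriptive. That limits the consequence, and it is accepted.

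A reader might also infer from the 2.5% in the text and `alpha=0.05` in the code that the test level is contradictory. The documents largely settle this. Protocol 10.4 plans its between-group power at one-sided 2.5%, and SAP 11.2.3 makes all confidence intervals two-sided 95%. The simulated Dunnett critical value is 2.35 for both one-sided 2.5% and two-sided 5%. Only the word one-sided is missing.

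None of this answers the quadratic contrast, which is wrong under the very coding the defence relies on.

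**Conclusion.** The point holds in two parts. First, the code relies on a placebo-first coding that the SAP does not define and that conflicts with its only group numbering; the two must be reconciled. The damage in steps 5 and 6 is conditional on `group` following the section 10 numbers, and its size rests on assumed rises over placebo.

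Second, and without any such condition, at least one printed trend contrast is wrong under every level order. Under placebo-first coding it is the quadratic, which largely repeats the linear test. The 99% figure assumes a response linear in dose and SD 0.4; the 0.87 correlation needs equal group sizes only. Because SAP 6.3.2 bases the AUC analysis on a similar program, the error would carry over to the AUC trend.

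No primary endpoint is affected: the primary objective is safety. The trend code needs correcting before the unblinded analyses; the sidedness of 2.5% is a minor clarification.

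**What to change.** State in SAP 6.3.1.2 how `group` is coded in `sero` and the CLASS level order, and identify the placebo reference by label, `control('Placebo')`, or by the matching coded value. Then set the contrasts to that order:

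- Placebo, 30, 60, 120: Linear `0 -4 -1 5`, Quadratic `0 2 -3 1`.
- Section 10 order (30, 60, 120, Placebo): `control('4')`, Linear `-4 -1 5 0`, Quadratic `2 -3 1 0`.

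Switching to text labels without fixing the level order would bring in the alphabetical sort of step 7, so reference and order should be changed together. Apply the same correction to the AUC program. Give the coefficients with their level order in the footnotes of Templates 52 and 53. Add that alpha = 2.5% is one-sided, consistent with the two-sided 95% interval.

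The cost is a few code lines, two footnotes and a sentence. No data collection or sample size changes.

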6.4. Analysis of safety

6.4.1. Analysis of safety planned in the protocol

The analysis of safety will be performed on the ES.

6.4.1.1. Within group analysis

The percentage of subjects with at least one **local AE** (solicited and unsolicited), with at least one **general AE** (solicited and unsolicited) and with any AE during the 7-day or 30-day follow-up period after vaccination will be tabulated with exact 95% CI. The same computations will be done for any \geq Grade 2 AEs, for any AEs considered related to vaccination, for any Grade 3 AEs considered related to vaccination and for AEs resulting in medically attended visit.

The percentage of subjects reporting each individual **solicited local AE** (any, each grade, resulting in medically attended visit) during the 7-day follow-up period after vaccination will also be tabulated based on maximum intensity per subject for each study vaccine group. The percentage of subjects reporting each individual **solicited general AE** (any, each grade, any related, any Grade 2 related, any Grade 3 related, resulting in medically attended visit) during the 7-day follow-up period after vaccination will also be based on maximum intensity per subject for each study vaccine group.

For fever during the 7-day follow-up period after vaccination, the number and percentage of subjects reporting any fever and fever by half degree ($^{\circ}\text{C}$) cumulative increments will be reported. Similar tabulations will be performed for causally related fever, Grade 3 causally related fever and fever resulting in a medically attended visit. In addition, the prevalence of any and Grade 3 fever will be presented graphically over time after vaccination.

The percentage of subjects with any **unsolicited** symptoms within 30 days after vaccination with its exact 95% CI will be tabulated by group and by MedDRA System Organ Class and preferred term. Similar tabulation will be done for Grade 3 unsolicited symptoms, for any causally related unsolicited symptoms, for Grade 3 causally related unsolicited symptoms and for unsolicited symptoms resulting in a medically attended visit (the verbatim reports of unsolicited symptoms will be reviewed by a physician and the signs and symptoms will be coded according to the MedDRA Dictionary for Adverse Reaction Terminology. Every verbatim term will be matched with the appropriate Preferred Term).

SAEs reported throughout the study will be described in detail.

Pregnancy exposures throughout the study and pregnancy outcomes will be described in detail (if applicable).

The percentage of subjects using **concomitant medication** (any medication, any antipyretic and any antipyretic taken prophylactically, respectively) during the 7-day follow-up period (Day 1 - 7), 30 days follow-up (Day 1 – 30), between Day 1 – Day 91 and between Day 1- Day 181 after vaccination, will be summarized by group.

For all subjects in each group and each **haematology and biochemistry** parameter:

- The percentage of subjects having haematology and biochemistry results below or above the local laboratory normal ranges will be tabulated for each time point.
- The maximum grading post-vaccination (up to Day 8 and up to Day 31) versus baseline (Screening) and the percentage of subjects with laboratory parameters above or equal to Grade 1, Grade 2, Grade 3 and Grade 4 will be tabulated (Grades will be based on the FDA Guidance for Industry “Toxicity Grading Scale for Healthy Adult and Adolescent Volunteers Enrolled in Preventive Vaccine Clinical Trials”, see [Table 4](#) and [Table 5](#): FDA toxicity grading scale. Those laboratory parameters not included on FDA Toxicity Grading Scale will not be graded).

